2.1.1 General definitions

Study treatment, study medication or study drug

In this document, “study treatment”, “study medication” or “study drug” refers to the investigational, control drug or placebo of this study. Run-in study treatment, study medication or study drug refers to placebo matching LIK066/placebo matching Empagliflozin assigned to the patients during placebo run-in; double-blind study treatment, study medication or study drug refers to LIK066 2.5mg qd, LIK066 10mg qd, LIK066 50mg qd, Empagliflozin (up-titrated from 10mg qd to 25mg qd after 2 weeks) or placebo matching LIK066/placebo matching Empagliflozin assigned to a patient at randomization.

Run-in period

Run-in period refers to Epoch 2 (placebo run-in).

Double-blind period

Double-blind period refers to Epoch 3 (treatment period 1) + Epoch 4 (treatment period 2).

Baseline and study day

Baseline is defined as the last measurement obtained before or at the randomization visit. The first day of administration of randomized study treatment (first dose) is defined as Day 1 for the study. If the date of first administration is missing, then randomization date will be used as Day 1.

All other study days will be labeled relative to Day 1. For event dates on or after Day 1, study day for a particular event date is calculated as [Date of event] – [Date of first dose] + 1. For the dates before Day 1, study day for an event date is calculated as [Date of event] – [Date of first dose]. Duration of an event will be calculated as [Event end date] – [Event start date] + 1. The descriptor “Day 0” will not be used.

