2.6.2.2 Adverse events of special interest / grouping of AEs

AEs of special interest that are defined in the Development Safety Profiling Plan (DSPP) can be found in the electronic case retrieval sheet (eCRS) stored in GPS.

The pre-defined issues of special interest for LIK066 including identified risks, potential risks and special assessments are listed below:

- Bone fractures
- Cardiotoxicity
- Diarrhea
- Electrolyte disturbances
- Genital infections
- Hepatotoxicity
- Hypersensitivity
- Hypoglycemia
- Impaired renal function
- Increased LDL
- Intravascular volume depletion

- Ketoacidosis
- Lower limb amputation
- Pre-amputation events
- Malignancy
- Pancreatitis
- Urinary tract infections
- Venothrombotic and embolic events

Treatment-emergent AEs of special interest will be summarized for double-blind period, by risk category, preferred term and treatment group. Treatment emergent AEs of special interest during the double-blind period will also be summarized descriptively by risk category, preferred term and treatment group in the following subgroups: baseline LVEF < 45% vs. \geq 45%.

Additional analyses for the pre-defined risks of diarrhea, ketoacidosis and hypoglycemia will be performed as described below:

Diarrhea events

Number of days with diarrhea events will be calculated for all patients with at least one diarrhea incidence and will be summarized descriptively by treatment.

- Number of days for one diarrhea incidence = AE end date – AE start date +1.
- Number of days with diarrhea events for a patient = sum of days on diarrhea over all incidences that occurred in the double-blind period.

The number and percentage of patients with diarrhea events during the double-blind treatment period will also be summarized by treatment over time in the following time window: 0 - < 2, 2 - < 4, 4 - < 8, 8 - < 12, 12 - < 16, 16 - < 24, \geq 24 weeks.

Ketoacidosis events of special interest

All cases of ketoacidosis will be adjudicated by an independent committee. The frequencies and percentages of the adjudication confirmed ketoacidosis events will be provided by treatment.

The site-reported ketoacidosis events will also be summarized by treatment. In addition, the ketoacidosis events will be listed at individual patient level, with the site-reported event profile and symptoms and the adjudication outcome displayed as well.

Hypoglycemic events of special interest

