5.1.2 AE date imputation

AE end date imputation

1. If ‘month’ is missing, the end date will be set to the earliest of the (min (last visit date, last dose date), 31DECYYYY, and date of death).
2. If ‘day’ is missing, the end date will be set to the earliest of the (min (last visit date, last dose date), 31MONYYYY, and date of death).
3. If ‘year’ is missing or AE is ongoing, the end date will not be imputed.

AE start date imputation

Before imputing AE start date, find the AE start reference date.

- If the (imputed) AE end date is complete and the (imputed) AE end date < treatment start date then AE start reference date = min (informed consent date, earliest visit date).
- Else AE start reference date = treatment start date

After finding the AE start reference date:

1. If 'year' is missing, the date uncertainty is too high; therefore the imputed AE start date will be set to NULL.
2. If 'year' is less than the treatment start date 'year', the AE started before treatment; therefore:
 - a. If 'month' is missing, the AE start date will be set to 01JULYYYY.
 - b. If 'day' is missing, the AE start date will be set to 15 MONYYYY.
3. If 'year' is greater than the treatment start date 'year', the AE started after treatment; therefore:
 - a. If 'month' is missing, the AE start date will be set to 01JANYYYY.
 - b. If 'month' is not missing, the AE start date will be set to the later of (01MONYYYY, AE start reference date + 1).
4. If 'year' is equal to the treatment start date 'year'
 - a. If 'month' is missing, the AE start date will be set to the AE reference start date +1.
 - b. If 'month' is less than the treatment start 'month', the AE start date will be set to 15MONYYYY.
 - c. If 'month' is equal to or greater than the treatment start 'month', the AE start date will be set to the later of (01MONYYYY, AE start reference date+1).

If complete (imputed) AE end date is available and the imputed AE start date is greater than the (imputed) AE end date, imputed AE start date will be set to the (imputed) AE end date.

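### SAP 5.1.2 can give a partly dated diarrhoea episode that starts after last dose zero or negative days, and gives an ongoing episode no days at all

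*SAP*

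**What the plan says.** SAP 2.6.2.2 singles out diarrhoea for a duration summary. It states that "Number of days with diarrhea events will be calculated for all patients with at least one diarrhea incidence". An episode's length is "Number of days for one diarrhea incidence = AE end date – AE start date +1", and a patient's value is the "sum of days on diarrhea over all incidences that occurred in the double-blind period". SAP 2.1.1 sets that period: "Double-blind period refers to Epoch 3 (treatment period 1) + Epoch 4 (treatment period 2"). It is not cut at last dose.

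SAP 5.1.2 supplies the AE end dates. With the day missing, the date is "set to the earliest of the (min (last visit date, last dose date), 31MONYYYY, and date of death"). With the month missing, it is "set to the earliest of the (min (last visit date, last dose date), 31DECYYYY, and date of death"). Where the year "is missing or AE is ongoing, the end date will not be imputed". A closing check handles a start later than the end, but only for starts that were themselves imputed: the "imputed AE start date will be set to the (imputed) AE end date". SAP 5.1.3, for concomitant medication, has the safeguard that 5.1.2 lacks: an imputed end date that falls before the start date is moved up to the start date.

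Episodes after last dose are in scope. SAP 2.6.2.1 gives treatment-emergent events a lower limit at first dose and no upper limit at last dose. Protocol 5.6.2 keeps patients in the study after drug is stopped and continues AE collection, by clinic or telephone visit.

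**The concern.** Two rules do not fit together. The summary counts episodes over the whole double-blind period, while the end-date rule treats last dose as the latest possible end. For a patient who stops drug early and is still followed, the imputed end can therefore fall before the month that the site recorded, or before the known start. The formula then returns too few days, zero days or a negative number. A negative number does more harm than a missing one, because it cancels real days from the patient's other episodes.

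The summary also promises a value for every patient with an episode, but an ongoing episode, or one with no end year, has no end date to put into the formula. The SAP does not say how to form a total when one episode has no value.

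Protocol 3.3 names limiting diarrhoea as a reason for the choice of top dose and for bedtime dosing, and this is the only planned summary of how long diarrhoea lasts. Episodes that persist, or that occur around drug stop, are relevant to tolerability.

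**Working it through.** The plan gives no figure to reproduce, so the check applies its rules to example dates.

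**Inputs from the documents:** the episode formula and the sum (SAP 2.6.2.2), the end-date rules and closing check (SAP 5.1.2), and follow-up to V299 for patients who stop drug in Epoch 3 (Protocol 5.6.2).

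**Assumed:** a 365-day year; randomised 12 Feb; last dose 5 Mar; last visit is V299 at 12 weeks, 12 Feb + 84 days = 7 May; no death; complete start date; end recorded as April with the day missing; 31MONYYYY read as the last day of the month.

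**Step 1, imputed end.** min(7 May, 5 Mar, 30 Apr) = 5 Mar, which lies outside the recorded month.

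**Step 2, days.**

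| Start | Rule as written | Record allows (end 1 to 30 Apr) |
|---|---|---|
| 1 Mar | 5 − 1 + 1 = 5 | 32 to 61 |
| 6 Mar | 5 − 6 + 1 = 0 | 27 to 56 |
| 20 Mar | 5 − 20 + 1 = −14 | 13 to 42 |

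**Step 3, general form.** Take a complete start k days after last dose. The recorded month or year cannot end before the start, so with no death and a last visit on or after last dose, last dose is always the smallest term. Days = last dose − (last dose + k) + 1 = 1 − k: 0 at k = 1, and negative from k = 2.

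**Step 4, patient total.** Add an earlier, completely dated 5-day episode to the 20 Mar one: 5 + (−14) = −9, where the record allows 5 + 13 = 18 to 5 + 42 = 47.

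**Step 5, closing check.** If the start is also partial (April), it is imputed as 1 Apr and then moved back to 5 Mar, giving 1 day. Zero or negative values therefore need a complete start date.

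**Step 6, proposed rule.** The floor alone gives 1 day for the 6 Mar and 20 Mar starts and leaves the 1 Mar start at 5. With last dose removed from the cap, the end is min(30 Apr, 7 May) = 30 Apr, giving 61, 56 and 42: the top of each possible range. Boundary case: start 10 Mar, last dose 15 Mar, end recorded as March. Neither the start nor 1 Mar falls after last dose, so the present rule stays and gives 15 − 10 + 1 = 6, inside the possible 1 to 22.

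**Step 7, ongoing episodes (illustration only).** Assume entry uniform over the 52 weeks before termination, follow-up of at most 252 days, constant onset rate, and exponential durations with mean m. The open share is E[exp(−(R + L)/m)], where R, the time from onset to the end of the period, has density proportional to 1 − r/364 on 0 to 252 days, and L is extra follow-up in days.

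| L | m = 7 | m = 14 | m = 30 |
|---|---|---|---|
| 0 | 4% | 8% | 17% |
| 30 | 0.1% | 1% | 6% |
| 90 | 0% | 0.01% | 0.8% |

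**The case against.** The case for leaving the text alone is fair on weight. The table is one descriptive summary in an abbreviated report after early termination; Protocol 9.5.2 does not ask for it, and no objective or test depends on it. Occurrence of diarrhoea is covered by the incidence and discontinuation tables, and every AE is listed by patient. Protocol 7.1 requires follow-up until resolution or until the event is judged permanent, so few episodes should stay open. Protocol 8.2 and 8.3 provide automatic checks and site queries, which should make partial dates uncommon. The opening of SAP section 5 says AE dates follow a sponsor standard, with details in a programming specification that was not supplied and may contain a safeguard. All of this stands. It lowers the weight of the point but does not repair the text: 5.1.2 states its rule explicitly and has no floor, while 5.1.3 has one.

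Three stronger readings are tempting, and the documents do not support them.

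- *The report will contain negative durations, or the comparison of arms is biased.* No counts of ongoing or partly dated episodes are given, by arm or overall, and the specification is unseen.
- *Many patients will have no value.* The higher shares in step 7 assume no follow-up beyond the period. Under follow-up to resolution the loss is close to nil.
- *Month-end imputation is an error because it overstates days on drug.* With last dose and last visit on 31 Oct, a start on 3 Apr and an end in April gives 28 days, inside the possible 1 to 28. That is an ordinary convention and can stay.

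**Conclusion.** The point holds as a minor error in the text. Followed literally, 5.1.2 and 2.6.2.2 together give 1 − k days to an episode with a complete start k days after last dose and a partial end date. They cut an episode continuing into a later recorded month before that month begins, and they leave ongoing episodes and those without an end year with no value.

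The impossible values need three things together: early drug stop with continued follow-up, onset after last dose, and a partial end date that survives data queries. How often that happens cannot be known from the documents.

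The duration formula feeds only the diarrhoea-days summary. The SAP does not say whether the diarrhoea time-window table counts onset or presence; confining the effect to one summary assumes onset. Confidence is high that the text has the gap, and low that it would visibly change the reported results.

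**What to change.** 1. In SAP 5.1.2, add the floor already in 5.1.3, so that an imputed AE end date is never earlier than a known start date.
2. In SAP 2.6.2.2, for this table only, apply a different cap where a complete start date, or the first day of the recorded end month, falls after last dose. There, replace last dose by the end of the double-blind period. The end date becomes the earliest of the recorded month or year end, last visit (including telephone), death, and end of the period. Label the value as imputed, at the top of its possible range. In all other cases keep the 5.1.2 rule.
3. For this table, cut ongoing episodes at the earliest of last visit, death and end of the double-blind period, and label them as minimum values. Report by arm the number of episodes that are ongoing or have no end year.

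The month-end convention for patients still on drug is unchanged.

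Cost: a few lines of SAP text and a small derivation change, with no new data. The downside is that some AEs will carry two end-date derivations, and one table will contain labelled minimum or upper values. The floor alone would remove the impossible values but would still leave post-dose episodes far too short (1 day in the 6 Mar and 20 Mar examples), so item 2 is worth the extra wording.

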2.6.2.3 Laboratory data

2.6.2.3.1 Hematology, Biochemistry and Urinalysis

Each laboratory parameter in [Table 2-3](#) will be summarized descriptively by visit and treatment group for actual and change from baseline values. The summary will be provided separately for biochemistry, hematology and urinalysis laboratory parameters.

Shift tables based on the standard ranges for each laboratory parameters will be provided by treatment group at each visit to present incidence of transitions from a baseline high, normal or low laboratory value to a post-baseline high, normal or low value.

The number and percentage of patients with clinically notable laboratory results post baseline will be presented in accordance with [Table 2-4](#).

Table 2-3 Laboratory parameters

Category	Parameter(s)
Hematology	RBC (total), WBC (total), platelet count (direct), hemoglobin, hematocrit, basophils (absolute, %), eosinophils (absolute, %), lymphocytes (absolute, %), monocytes (absolute, %), neutrophils (absolute, %)
Biochemistry	ALT, albumin, alkaline phosphatase (ALP), AST, bicarbonates, bilirubin (direct, total), blood urea nitrogen (BUN), calcium (total), chloride (Cl ⁻), creatinine, cystatin C, eGFR (MDRD), magnesium (Mg ²⁺), phosphates, potassium (K ⁺), protein (total), sodium (Na ⁺), uric acid, γ-GT, amylase, lipase, serum ketones and beta hydroxybutyrate
Urinalysis	pH, specific gravity, protein, glucose, ketones, nitrites, blood, leucocytes
Urinalysis	UACR Urine albumin to creatinine ratio (spot urine), cystatin C/creatinine ratio (spot urine)

Table 2-4 Clinically notable laboratory values

Parameter	Criteria (based on a percent change from baseline)
Hematology	
RBC (total)	>50% increase, >20% decrease
WBC (total)	>50% increase, >50% decrease
Platelet count	>75% increase, >50% decrease
Hemoglobin	>50% increase, >20% decrease
Hematocrit	>50% increase, >20% decrease
Clinical chemistry	
ALT	>150% increase
AST	>150% increase
BUN	≥50% increase
Creatinine	>50% increase
Total bilirubin	>100% increase
ALP	>100% increase
Sodium	>5% increase or >150, or decrease <130 mmol/L

Potassium	absolute values < 3.0 mmol/L, > 5.9 mmol/L
Chloride	>10% increase, >10% decrease
Calcium	>10% increase, >10% decrease and hyper - > 2.6,
Uric acid	>50% increase
Plasma glucose	>50% increase
Plasma glucose	< 3.0 mmol/L (54 mg/dL)

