Sodium-glucose co-transporter (SGLT) 2 inhibitors are approved for the treatment of type 2 diabetes. In addition, long-term treatment with the SGLT2 inhibitor empagliflozin in the EMPA REG Outcome study resulted in 14% relative reduction (RR) in major adverse cardiovascular events (MACE) vs placebo driven by a statistically significant 38% RR in cardiovascular (CV) death. The risk of hospitalizations for HF was also reduced (Zinman et al, 2015). In this study, patients with eGFR down to 30 ml/min/1.73m^2 were included. In a subgroup analysis by renal function categories, the risk of CV death or HF hospitalization was significantly reduced in the groups with mild and moderate renal impairment. This composite endpoint was also significantly reduced in patients without previously diagnosed HF, and was numerically lower in patients with HF at baseline, who comprised approximately 10% of the study population (Fitchett et al, 2016). It is hypothesized that the observed benefit may have derived from the specific effects of SGLT2 inhibition on renal sodium and glucose handling, leading to both diuresis and improvements in diabetes-related maladaptive renal arteriolar responses (Sattar et al, 2016), from the switch of free fatty acids oxidation in the heart to the more efficient beta-hydroxybutyrate oxidation, as well as from the enhanced oxygen supply due to hemoconcentration (Ferrannini et al, 2016).

LIK066 is an inhibitor of SGLT1 and SGLT2. Via inhibition of both SGLT1 and SGLT2 in the proximal renal tubule, the drug may further enhance the effects on renal sodium and glucose handling compared with the selective SGLT2 inhibitors. In addition, SGLT1 is expressed in the small intestine where it is required for glucose and galactose absorption. Inhibition of enteric SGLT1 results in glucose and galactose malabsorption (Turk et al, 1991) which leads to calorie wasting and other potential endocrine-based weight loss mechanisms. Considering its dual mode of action (renal and intestinal) on re-absorption/absorption of glucose, LIK066 is planned for investigation in obese and overweight patients as a weight loss drug (calorie-loss enhancer). In a phase I study with normo- and dysglycemic adults with body-mass index (BMI)  $\geq 35\text{kg/m}^2$ , treatment with LIK066 150mg qd resulted in a mean 5.7% placebo subtracted weight loss at 12 weeks [Data on file].

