### 4.1 Inclusion criteria

Patients eligible for inclusion in this study must fulfill all of the following criteria:

1. Written informed consent must be obtained before any assessment is performed.
2. Male or female outpatients,  $\geq 18$  years of age at Visit 1.
3.  $\text{BMI} \geq 22 \text{ kg/m}^2$  at Visit 1.
4. Type 2 diabetes with  $\text{HbA1c}$  between 6.5% and 10.0% at Visit 1.
5. Documented symptomatic chronic heart failure (NYHA II-IV) with at least one of the following symptoms at the time of Visit 1:
  - Dyspnea on exertion
  - Orthopnea
  - Paroxysmal nocturnal dyspnea
  - Peripheral edema
6. Plasma NT-proBNP  $> 300 \text{ pg/ml}$  at Visit 1.
7. Patients receiving ACEi, ARBs, MRAs, ARNi and/or  $\beta$ -blockers must be on a stable dose of these medications during the 1 month period prior to Visit 1.
8. Patients must be on diuretic therapy prior to Visit 1 (flexible dosing is permitted).
9. Controlled systolic BP defined as a target systolic BP less than 140mmHg; systolic BP up to and including 160mmHg if patient is on three or more medications to control BP, at randomization (Visit 201).
10.  $\text{eGFR} \geq 45 \text{ ml/min/1.73m}^2$  at Visit 1 (calculated by the Modification of Diet in Renal Disease formula (MDRD)).
11. Serum potassium  $\leq 5.3 \text{ mM}$  at Visit 1.

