18. Hemodynamically significant mitral and/or aortic valve disease.
19. Hemodynamically significant obstructive lesions of left ventricular outflow tract, including aortic stenosis.
20. Hypertrophic obstructive cardiomyopathy.
21. Secondary forms of cardiomyopathy such as restrictive cardiomyopathy or infiltrative cardiomyopathy (e.g., amyloid disease).
22. Patients with a history of any organ transplant or who were on a transplant list (life expectancy < 6 months at time of entry into the study).
23. Patients with a mean sitting systolic blood pressure  $\leq$  100mmHg, at Visit 201 (randomization).
24. Patients with an implantable medical device (e.g. cardioverter defibrillator (ICD)) that has discharged in the month prior to Visit 1.
25. Episode(s) of malignant ventricular tachycardia or any other types of severe arrhythmia producing significant hemodynamic consequences or considered life-threatening within 3 months of Visit 1.

26. Acute or chronic liver disease (except liver steatosis), such as hepatitis, cirrhosis or portal hypertension at Visit 1 or Visit 201 (randomization).
27. History of hepatitis B or C, or Hepatitis A or B vaccination in the last 3 months prior to Visit 1, or between Visit 1 and Visit 201 (randomization).
28. Active substance abuse, alcohol abuse (as defined by consumption of more than 24 alcohol units per week) and alcohol related history of disease within the past 2 years.
29. Chronic treatment with medication which has a hepatotoxic potential.
30. Chronic use of anti-retroviral therapies.
31. Chronic use of strong CYP3A4 inhibitors (e.g. clarithromycin, telithromycin, itraconazole, ketoconazole, voriconazole or posaconazole) or chronic use of strong uridine-5'-diphosphoglucuronosyltransferase (UGT) inhibitors (e.g. probenecid, valproic acid or mefenamic acid).
32. Concurrent medical condition that may interfere with the interpretation of efficacy and safety data.
33. Clinically significant thyroid stimulation hormone (TSH) level outside of the normal range at Visit 1.
34. Alanine aminotransferase (ALT), or aspartate aminotransferase (AST) more than three-fold above upper limit of normal ( $>3 \times \text{ULN}$ ), or total bilirubin/direct bilirubin  $> 1.5 \times \text{ULN}$  at Visit 1, confirmed by repeat measurement within 5 working days of the respective visit.
35. Hemoglobin  $< 11\text{g/dL}$  in men,  $< 10\text{g/dL}$  in women at Visit 1 (screening).

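### The >50% rise limit for red-cell measures in SAP Table 2-4 makes the high-side clinically notable count uninformative about hemoconcentration (minor)

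*SAP*

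**What the plan says.** SAP 2.6.2.3.1 plans three outputs for hematology:

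- descriptive summaries of actual values and changes from baseline, by visit and arm;
- low/normal/high shift tables, by arm at each visit;
- a patient-level count: "The number and percentage of patients with clinically notable laboratory results post baseline will be presented in accordance with" Table 2-4.

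The limits in Table 2-4 are headed "Criteria (based on a percent change from baseline"). The rows for red cell count, hemoglobin and hematocrit all carry the same entry, ">50% increase, >20% decrease". Other rows have their own limits: 10% either way for chloride, 50% either way for white cells, absolute values for potassium. The three red-cell rows have no absolute upper limit, and neither document gives a reason for 50%.

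For context, Protocol 1.1 lists, among hypothesized sources of the class benefit, "as well as from the enhanced oxygen supply due to hemoconcentration". Protocol 4.1 adds "Patients must be on diuretic therapy prior to Visit 1". The issues of special interest in SAP 2.6.2.2 include intravascular volume depletion and "Venothrombotic and embolic events".

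**The concern.** A rise is the direction that the protocol's own background associates with this drug class, in a population that is all on diuretics. Yet the fall is guarded by a 20% limit and the rise by a 50% limit. If the high limit is out of reach at usual baselines, the clinically notable table will print about 0% in every arm whether or not the drug concentrates the blood. A reader of the abbreviated report could take that row as evidence of no marked rises, when it could hardly have shown anything else.

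**Working it through.** The limit is a fixed reporting threshold with no derivation, so there is no plan figure to reproduce. The check is what the limit implies.

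**1. Implied values (limit = 1.5 × baseline).** The baselines are assumed, except for the hemoglobin entry floors in Protocol 4.2 (11 g/dL men, 10 g/dL women, at Visit 1).

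| Parameter | Baseline | Limit |
|---|---|---|
| Hematocrit | 30% | >45% |
| Hematocrit | 40% | >60% |
| Hematocrit | 45% | >67.5% |
| Hemoglobin, women's floor | 10 g/dL | >15.0 g/dL |
| Hemoglobin, men's floor | 11 g/dL | >16.5 g/dL |
| Hemoglobin | 14 g/dL | >21.0 g/dL |

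**2. Plasma loss needed by hemoconcentration alone.** With red-cell mass constant, raising hematocrit from h to 1.5h means blood volume falls to 1/1.5 of its start. One third of blood volume is lost, all of it plasma, so the fraction of plasma lost is (1/3)/(1 − h). This is 48% at h = 0.30, 56% at 0.40 and 61% at 0.45. For a 20% rise at h = 0.40 it is (1/6)/(0.60) = 28%.

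**3. Chance of crossing at one visit.** Assumed: baseline hematocrit 40%, normally distributed change, SD 2.5, 3.0 or 3.5 points, mean change 0, 2 or 3 points. A 50% rise is 20 points; a 20% rise is 8 points.

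- Above 50%, worst case: z = (20 − 3)/3.5 = 4.86, P about 6e-7.
- Above 20%:

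| Mean change | SD 2.5 | SD 3.0 | SD 3.5 |
|---|---|---|---|
| 0 points | 0.0007 | 0.0038 | 0.0111 |
| 2 points | 0.0082 | 0.0228 | 0.0432 |
| 3 points | 0.0228 | 0.0478 | 0.0766 |

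**4. Wider range.** Let the mean rise run from 0 to 10% and the SD from 5 to 12% of baseline. The worst corner (10%, 12%) gives z = 40/12 = 3.33 and P = 4.3e-4. That is 124 × 4.3e-4 = 0.05 patients per visit in an arm of 124, and 0.21 in all 496. With six scheduled visits after randomization (Weeks 2 to 36), an upper bound for any visit is 6 × 0.053 = 0.32 per arm of 124 and 6 × 0.21 = 1.3 in the whole planned study. At a mean of 5% and SD of 8%, the per-visit figure is about 1e-6 per arm.

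**5. Asymmetry.** On the log scale the limits are ln(1.5) = 0.41 and ln(0.8) = −0.22. The reciprocal of a 20% fall is a 25% rise.

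**6. What the other outputs add.** Under SAP 2.1 continuous summaries include Q3 and the maximum, so the largest rise per arm and visit will be printed. The shift tables count normal-to-high moves per arm and visit. Neither gives the number of patients with a marked rise at any post-baseline visit, and a large rise that stays within the normal range does not appear as a shift.

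**The case against.** The strongest reply is that Table 2-4 is one output among several. Shift tables count patients moving to high, by arm. The change summaries show the extremes. Clinically significant laboratory findings become adverse events under Protocol 7.1, and volume depletion and thromboembolic events are tabulated by arm. All of that stands. A reader might infer that hemoconcentration will go unseen in the report; the documents do not support this.

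A reader might also infer that the limit can never be met. At the entry floors it is only 15.0 to 16.5 g/dL, and the floors apply at Visit 1 whereas "Baseline is defined as the last measurement obtained before or at the randomization visit", so an analysis baseline could be lower still. A patient whose anemia is corrected could cross it, although that would mostly not be hemoconcentration.

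Nor do the documents name hemoconcentration as a safety risk. Protocol 1.1 offers it as a hypothesized mechanism of benefit, it is not on the SAP list of special-interest issues, and a link to thromboembolism would be the reader's inference.

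Finally, a 20% threshold is not shown to separate the arms. At 2.3% against zero, about 3 of 124 against 0 of 124 gives a two-sided Fisher p of about 0.25, and that uses planned arm sizes in a study that ended early. The 20% figure is a convenient match to the size of the fall limit, with no other basis in the documents.

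What remains is narrower: the one patient-level, any-visit count of marked change is set where its high side carries almost no information.

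**Conclusion.** The point holds in limited form. At usual baselines the high-side count for red cell count, hemoglobin and hematocrit will be at or near zero in every arm, so it cannot distinguish the arms and a zero there should not be read as reassurance. The change summaries and shift tables remain the places to look, but they leave out the number of patients with a marked rise at any time after baseline.

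The size rests on assumed baselines, means, SDs and normal tails, none of which the documents give. The conclusion of near zero survives the whole range tried; the exact probabilities do not carry weight. Severity is minor: no test, power figure or primary analysis depends on the limit, and the output is descriptive reporting in an abbreviated study report after early termination.

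**What to change.** Keep the >50% entry if it is a company standard. For red cell count, hemoglobin and hematocrit, add a lower high-side reporting threshold to Table 2-4, for example >20% increase, matching the size of the existing fall limit. Report on its own line, by arm, the number and percentage of patients who meet it at any post-baseline visit. If the sponsor prefers the limit as it is, a sentence of justification and a pointer to the change and shift tables would prevent misreading.

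This is a descriptive reporting threshold and carries no implication for treatment. The cost is three table entries and one programming parameter, using data already collected. The downside is more flagged patients to review: under the assumptions in step 3, about 1 to 9 per visit in an arm of 124 with a drug effect (124 × 0.0082 = 1.0; 124 × 0.0766 = 9.5), and fewer in practice because the study stopped early.
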